3.3.3. Other Efficacy Endpoints

These analyses will be conducted on the ITT population and the efficacy-evaluable population.

The description of overall moroctocog alfa (AF-CC) efficacy will be based on the number of infusions per bleed, assessment of the response of bleed to treatment, time interval between bleed onset and prior moroctocog alfa (AF-CC) treatment, incidence of prophylaxis regimen escalation, incidence of less-than expected therapeutic effect (LETE), consumption of moroctocog alfa (AF-CC) and compliance with assigned prophylaxis regimen. Descriptive statistics will be provided for each of these endpoints; statistical hypothesis tests will not be conducted.

3.3.3.1. Number of Infusions per Bleed

Number of study drug infusions used to treat a bleed will be summarized by bleed location, by dose (IU/kg) administered at the first infusion.

3.3.3.2. Assessment of the Response of Bleed to Treatment

The 4-point response (efficacy rating) for study drug-treated bleeds will be summarized. The response to the first study drug infusion to treat a bleed will be tabulated by the total number of infusions needed for bleed resolution. First infusion responses will also be summarized by bleed location and by administered dose (IU/kg).

3.3.3.3. Time Between Bleed Onset and Prior Treatment

The time between onset of a bleed and prior moroctocog alfa (AF-CC) prophylaxis infusion will be summarized by the following categories: ≤ 24 , ≥ 24 -48, ≥ 48 -72, and ≥ 72 hours. If the onset time of a bleed is unknown, then a default time of "00:00" will be used in calculation. The number of bleeds will be classified by the type of bleed (spontaneous or traumatic) and summarized for each subject and overall and by prophylaxis regimen (A or B).

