Less than expected therapeutic effect, LETE (prophylaxis)	Less than Expected Therapeutic Effect (LETE) occurs in the prophylaxis setting if there is a spontaneous bleed within 48 hours (≤ 48 hours) after a regularly scheduled prophylactic dose of study drug (which was not used to treat a bleed) in the absence of confounding factors as described in this protocol.
Less than expected therapeutic effect, LETE (low recovery)	Lower than expected recovery of FVIII in the opinion of the investigator following injection of study drug in the absence of confounding factors as described in this protocol.
Medical records	Legal documentation (written or electronic) of a patient's medical history, current illness, diagnosis, treatments, and/or other medical data that is maintained by the investigator. For the purposes of this study, these can serve as source documents.
Modified intent-to-treat population	The modified intent-to-treat population consists of subjects who receive at least 1 dose of study drug (moroctocog alfa [AF-CC]).
Monitor	A person, with the appropriate qualifications and assigned by the Sponsor, to oversee the progress of a study, and to ensure that it is conducted, recorded, and reported in accordance with the protocol and other applicable requirements.
On-demand (OD) Subject	A study subject that practices on-demand therapy with moroctocog alfa (AF-CC) for the first segment of the study, followed by routine prophylaxis for the second segment.

Term	Definition
On-demand treatment	Treatment of hemorrhages, as needed, by administering an unscheduled bolus infusion of study drug to stop bleeding and control hemostasis.
Patient	For the purposes of this protocol, a person with hemophilia A.
Previously treated patients (PTPs)	Patients who have received FVIII replacement therapy. For the purposes of this study, PTPs are those who have accrued ≥20 exposure days to any FVIII replacement product.
Previously untreated patients (PUPs)	Patients who have not received any FVIII replacement therapy or any blood products.
Prophylaxis	FVIII replacement therapy administered at a routine interval such as every other day, for a prolonged period of time, to prevent occurrence of spontaneous musculoskeletal bleeding episodes.
Regimen A	Study drug prophylaxis regimen of 45 ±5 IU/kg, administered twice per week. The interval between prophylactic infusions should be 3 to 4 days, and should not exceed 4 days.

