## 16.3.2. Moroctocog alfa (AF-CC) Administration for Prophylaxis

Subjects will be advised to routinely administer the prophylaxis dose in the morning, in advance of their day's activities. The dose will be prepared using the actual potency on the label of the study drug to be administered and the subject's most recent actual body weight as measured during the study. See Study Reference Manual for guidelines of dose selection based on the subject's measured body weight.

Subjects will use moroctocog alfa (AF-CC) for prophylaxis according to the assigned regimen, A or B:

A: 45 ±5 IU/kg, administered twice per week

B: 25 ±5 IU/kg, administered every other day

For regimen A, the interval between prophylactic infusions should be 3 to 4 days, and should not exceed 4 days. For regimen B, the interval between prophylactic infusions should be approximately 48 hours (eg, an appropriate dosing schedule for Regimen B is as follows Monday, Wednesday, Friday, Sunday, Tuesday, Thursday, Saturday, Monday...etc).

The dosage and dosing frequency of these regimens are consistent with ReFacto and moroctocog alfa (AF-CC) clinical data, and with recommendations for prophylactic dosing in the literature.  (See Study Reference Manual for specific dose selections for regimens A and B based on the subject's measured body weight). A subject's treatment will be escalated to a more intensive prophylaxis regimen (45 ±5 IU/kg, administered every other day, initially, and if dose escalation criteria are met while on this more intensive regimen the subsequent regimen escalation will be investigator-designated) if criteria justifying regimen

escalation are met (see Section 15.3.3). Guidance for prophylaxis treatment is offered in the investigator's brochure.

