# Additional efficacy variables:

- Number of study drug infusions used to treat a bleed will be summarized by bleed location and by dose (IU/kg) administered at the first infusion.
- The 4-point response (efficacy rating) for study drug-treated bleeds will be summarized, and any successive ratings of "*No Response*" will also be reported. The response to the first study drug infusion to treat a bleed will be tabulated by the total number of infusions needed for bleed resolution. First infusion responses will also be summarized by bleed location and by administered dose (IU/kg).
- The time between onset of a bleed and prior moroctocog alfa (AF-CC) routine prophylaxis infusion will be summarized by the following categories: ≤24, >24-48, >48-72, and >72 hours.
- The number (%) of subjects requiring prophylaxis regimen escalation during protocol-defined prophylaxis will be provided, and will be reported for each protocol-defined regimen.
- The number (%) of subjects reporting LETE (see Section 18.2) will be provided.
- For consumption of moroctocog alfa (AF-CC) per bleed, first infusion (IU/kg) and total dose (IU/kg) administered for the bleed will be summarized by bleed location (joint, soft tissue/muscle, multiple sites, and other). For consumption of moroctocog alfa (AF-CC) over time, the number of infusions, exposure days (ED), and dose (IU/kg and IU) per infusion will be summarized by reason of dosing (ie, on-demand or prophylaxis). Descriptive statistics (n, mean, SD, median, minimum, and maximum) will be provided.
- Descriptive statistics will be provided to summarize subject compliance to their assigned prophylaxis regimen (dose [IU/kg] and dose frequency [number of infusions per week]). The number of infusions and the number of days (and weeks) on each assigned prophylaxis regimen will be presented for each subject.

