3. ANALYSIS OF SAFETY AND EFFICACY ENDPOINTS

All data collected during the course of the study will be presented in a listing format.

In general, descriptive statistics will summarize all efficacy and safety endpoints as appropriate. For continuous variables, number, mean, standard deviation, median, minimum, and maximum will be provided. Interquartile ranges and 95% confidence intervals may be provided where meaningful. For categorical variables, frequency and percentage will be presented for each category.

Safety and efficacy analyses for the OD subject cohort (on-demand therapy in segment 1, followed by the prescribed prophylaxis regimen in segment 2), will be done independently from the analyses for the RP subject cohort (randomized to follow prophylaxis regimens in both segments 1 and 2). PK characterization will be presented for all subjects (in either cohort) who provided PK data. In addition, select tables will be provided for all subjects in the study, regardless of cohort. See Summary of Changes to Planned Analyses for the Final CSR (Item 8) for further discussion.

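### Bleeds by hours since the last prophylaxis dose are tabulated without time at risk, so the band counts cannot be read as bleeding risk or compared between Regimens A and B

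*SAP*

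**What the plan says.** The protocol's list of additional efficacy variables (22.5.3) states: "The time between onset of a bleed and prior moroctocog alfa (AF-CC) routine prophylaxis infusion will be summarized by the following categories". The bands are "≤24, >24-48, >48-72, and >72 hours". SAP 3.3.3.3 uses the same four bands and says what is tabulated: "The number of bleeds will be classified by the type of bleed (spontaneous or traumatic"), and then "summarized for each subject and overall and by prophylaxis regimen (A or B"). An unknown onset time is set to 00:00.

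SAP section 3 adds a general rule: "For categorical variables, frequency and percentage will be presented for each category". The percentages here would be shares of bleeds. Neither document plans hours at risk or a rate for each band. SAP 3.3.3.7 gives total infusions and total days on each regimen per subject, but does not split them by hours since dose.

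The dosing schedules are fixed in Protocol sections 4 and 16.3.2. Regimen A is given twice a week, and "the interval between prophylactic infusions should be 3 to 4 days, and should not exceed 4 days". Regimen B is given about every 48 hours. SAP 3.3.3 makes this endpoint descriptive, with no hypothesis test, on the ITT and efficacy-evaluable populations.

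**The concern.** The number of bleeds in a band depends on the bleeding rate in that band and on the time boys spend in it. The schedule sets the second factor, and the two regimens set it differently. A count or a share of bleeds therefore mixes dosing pattern with risk.

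This is the planned summary that shows how bleeds fall across the dosing interval, including beyond 48 hours. Prophylaxis LETE (less than expected therapeutic effect) covers only spontaneous bleeds within 48 hours of a dose. A reader who wants to know whether bleeding rises late in a 3- to 4-day interval will look here. Without denominators, a real but moderate rise after 72 hours on Regimen A could appear as a fall. The nearly empty late bands on Regimen B could be taken as evidence about risk when they reflect almost no exposure.

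**Working it through.** The plan states no figure for this table, so there is none to reproduce. The dose counts used below do agree with the plan: A gives 2 × 45 = 90 and B gives 3.5 × 25 = 87.5 IU/kg per week, against the stated approximate 90.

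**Method.** For a dosing interval of L hours, the time in a band from *lower* to *upper* is max(0, min(L, upper) − lower). The expected share of bleeds in a band is hours × relative rate, divided by the sum over bands.

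**Regimen A, full adherence.** Two intervals of 72 to 96 hours fill a 168-hour week.

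- Intervals of 72 + 96 give 48 / 48 / 48 / 24 hours.
- Intervals of 84 + 84 give the same.
- Shares of time are 48/168 = 28.6% for each of the first three bands and 24/168 = 14.3% beyond 72 hours.

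Let r be the bleeding rate beyond 72 hours relative to the other bands. The last band's share is 24r/(144 + 24r), and each other band's share is 48/(144 + 24r).

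| r | Beyond 72 h | Each other band |
|---|---|---|
| 1.0 | 24/168 = 14.3% | 28.6% |
| 1.25 | 30/174 = 17.2% | 27.6% |
| 1.5 | 36/180 = 20.0% | 26.7% |
| 1.75 | 42/186 = 22.6% | 25.8% |
| 2.0 | 48/192 = 25.0% | 25.0% |
| 3.0 | 72/216 = 33.3% | 22.2% |

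**In counts, for scale only.** Take 38 evaluable RP subjects (SAP 1.3.4) and 7.1 bleeds a year, the twice-weekly figure from study 301 in SAP 1.4.2. This gives 38 × 7.1 = about 270 bleeds.

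- A constant rate gives about 77 / 77 / 77 / 39.
- r = 1.5 gives about 72 / 72 / 72 / 54. The last count is 25% lower although the rate is 50% higher.

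**Missed Regimen A doses.** The documents give no rate, so this is an assumed range. With a fraction m missed, each of the first three bands holds 48(1 − m) hours a week, and the last holds 168 − 144(1 − m). The break-even r is the ratio of the two.

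| m | First three bands, each | Beyond 72 h | Break-even r |
|---|---|---|---|
| 0 | 48.0 h | 24.0 h | 2.00 |
| 5% | 45.6 h | 31.2 h | 1.46 |
| 10% | 43.2 h | 38.4 h | 1.13 |
| 12.5% | 42.0 h | 42.0 h | 1.00 |
| 15% | 40.8 h | 45.6 h | 0.89 |

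**Escalated time.** Suppose 10% of Regimen A time were on every-other-day dosing but still counted under A (an assumption). The first band would hold 0.9 × 48 + 0.1 × 84 = 51.6 hours and the last 0.9 × 24 = 21.6. This works in the opposite direction to missed doses.

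**Regimen B.** Intervals of 48 hours put all time in the first two bands, except around the 72-hour washouts. These fall at visits 3, 5, 7, 9 and 11 in segment 1, and at visits 13, 15, 17 and 19 in segment 2. A year has 365.25 × 24 = 8,766 hours. Each washout of 72 hours adds 24 hours to the third band.

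- 4 × 24/8,766 = 1.1%.
- 5 × 24/8,766 = 1.4%.

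The split is about 49 / 49 / 1.1–1.4 / 0%.

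**The case against.** The strongest reply is that the table carries little weight. The objective on dosing frequency is addressed by the within-subject A-versus-B difference in ABR (SAP 3.3.2). That endpoint already divides bleeds by days on regimen. SAP 3.3.3.7 adds an exploratory model with actual infusion frequency. The time-since-dose table is descriptive, no decision rule uses it, and it is already split by regimen and bleed type. Infusion times are recorded, so denominators could be derived later.

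Most of this stands. A reader might infer that this table is what answers the frequency question, or that its defect weakens the equivalence conclusion. The documents support neither. A reader might also infer that the band beyond 72 hours will look safest whatever the true risk. That is wrong too: it holds only for less than a two-fold rise under full adherence, and the limit falls as doses are missed.

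The reply does not supply a denominator for the bands. The SAP's percentages have the same defect as the counts, because they are shares of bleeds. Uncertain adherence strengthens the case for a denominator, since without observed hours a reader cannot tell even the direction of the distortion. Deriving the hours after results are known is possible, but it would leave the handling of escalated and surgical time to be chosen then.

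**Conclusion.** The point holds in a bounded form. As planned, the table cannot show how bleeding risk changes with time since dose, and its band percentages cannot be compared between A and B. The overall row adds two different exposure patterns together.

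On Regimen A with full adherence, the band beyond 72 hours has half the exposure of each other band. It shows fewer bleeds than each of them unless the rate there is at least double, with equality at exactly 2.0. This assumes a uniform rate across the first three bands and the schedule as written. The effect disappears at about 12.5% missed A doses and reverses above that. On Regimen B, the time beyond 48 hours is only about 1.1–1.4%, assuming washouts of 72 hours and no missed doses.

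The consequence is limited to interpreting one descriptive table. The primary comparison, the RP comparison of ABR and the equivalence test do not use it. The change is still worth making, because it is cheap and the table is otherwise easy to misread.

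**What to change.** Amend SAP 3.3.3.3 as follows:

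- From the infusion dates and times in the diary (Protocol 15.1.6 and 15.1.9), derive each subject's patient-time at risk in each band under each regimen.
- For each band and regimen, report bleeds, patient-time and bleeds per patient-year, by spontaneous and traumatic type.
- State one rule and apply it to bleeds and time alike. For example, keep the clock on the last prophylaxis infusion even when an on-demand infusion follows, exclude surgical periods, and show time after regimen escalation separately from A and B. Escalation needs stating because SAP 3.2.2.1 and 3.2.2.2 limit data to the originally prescribed regimen only for the per-protocol comparison populations, which this table does not use.
- Add a sensitivity table without bleeds whose onset time was defaulted to 00:00, since the default can move a bleed to a different band.
- Replace the pooled percentages with pooled rates.

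No test is needed, and the endpoint can stay descriptive. The cost is a little programming for one derived variable and a few extra columns. No new data are collected, and nothing in study conduct changes.

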3.3.3.4. Incidence of Prophylaxis Regimen Escalation

The number (%) of subjects requiring prophylaxis regimen escalation during protocoldefined prophylaxis will be provided by prophylaxis regimen (A or B).

Exploratory analysis, such as a time-to-escalation analysis, may be performed to characterize the timing and frequency of dose escalation, and the total dose used as a function of the treatment frequency (A or B) to which subjects were randomized.

3.3.3.5. Less-Than Expected Therapeutic Effect

3.3.3.5.1. Variable Definition

Criteria for LETE are evaluated by the investigator. If a potential LETE is identified, the date of the event along with information about the presence or absence of related confounding factors, which are defined in the protocol, will be recorded separately by LETE category. The three categories of LETE are defined as follows:

- 1. On-Demand LETE occurs if the subject records two successive "No Response" ratings after 2 successive infusions, respectively. The infusions must have been administered within 24 hours of each other for treatment of the same bleeding event in the absence of confounding factors.
- 2. Routine Prophylaxis LETE occurs if there is a spontaneous bleed within 48 hours after a regularly scheduled prophylactic dose (which was not used to treat a bleed) of study drug in the absence of confounding factors.
- 3. Low Recovery LETE occurs if, in the opinion of the investigator, lower than expected recovery is observed following injection of study drug in the absence of confounding factors.

3.3.3.5.2. Analysis Methods

A potential LETE outcome is reported by the investigator and will be reviewed using the definitions above. Sites will be queried if a potential LETE is identified in the review of the data but is not reported by the investigator or if there are any discrepancies in the assessments.

LETE will be determined by assessing the potential LETE cases for presence or absence of confounding factors. Each occurrence of LETE will be listed separately by type of LETE (on-demand, routine prophylaxis and low recovery).

The number (%) of subjects reporting LETE will be summarized overall and by regimen [on-demand and prophylaxis (A or B)].

3.3.3.6. Consumption of Moroctocog Alfa (AF-CC)

For consumption of moroctocog alfa (AF-CC) per bleed, the dose for the first infusion (IU/kg) and the total dose (IU/kg) administered for the bleed will be summarized by bleed location (joint, soft tissue/muscle, multiple sites, and other). For consumption of moroctocog alfa (AF-CC) over time, the total IU, the number of infusions, exposure days (ED), and dose (IU/kg and IU) per infusion will be summarized by reason of dosing (ie, on-demand or prophylaxis).

3.3.3.7. Compliance to Prophylaxis Regimen

Descriptive statistics will be provided to summarize subject compliance to their assigned prophylaxis regimen (dose [IU/kg] and dose frequency [number of infusions per week]). The number of infusions and the number of days (and weeks) on each assigned prophylaxis regimen will be presented for each subject.

As an exploratory analysis to determine the effect of non-compliance to regimen on ABR, the ANOVA model for the crossover design, described in SAP Section 3.3.2.2, will be fitted with an additional factor for actual treatment frequency (as opposed to prescribed frequency). Actual treatment frequency will be calculated from the number of infusions divided by the number of weeks on treatment, including non-routine prophylaxis infusions.

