# 15.1.6. Subject Activities Between Successive Study Visits (Visit 2 Through Visit 11), and Activities of Study Contacts 4, 6, 8, and 10 - Segment 1 - RP Cohort

Subjects will use moroctocog alfa (AF-CC) for hemophilia A treatment (protocol-defined prophylaxis [including treatment of any bleed, if necessary, during prophylaxis]). Subjects will document all of their infusions (dose, time of infusion, and reason) and all bleeding episodes in the Subject Diary. In addition, subjects will record the efficacy of a study drug infusion given on-demand for treatment of a bleed using a 4-point ordinal scale of "Excellent," "Good," "Moderate," and "No Response" in the Subject Diary (please refer to Section 18.1.3 for description of scale). Subjects will also document any AEs or use of concomitant medications in the Subject Diary. Subjects will save used study drug vials; used study drug vials are returned at each study visit. Approximately 4 weeks (±1 week) after study visit 3, and approximately 6 weeks ( $\pm 1$  week) after study visits 5, 7, and 9, respectively, the investigator (or designee) will contact the subject by telephone in order to collect information regarding the occurrence of any AEs, the use of concomitant medications, and study compliance. During these contacts, the investigator (or designee) will also review the subject's hemophilia A treatment (ie, investigator-prescribed on-demand therapy, or protocol-defined prophylaxis). The investigator (or designee) will also review information related to regimen escalation (criteria for, and subsequent action; see Section 15.3.3) with the

subject and will ensure that the criteria for regimen escalation had not been met. In addition, any change in a subject's prophylaxis regimen must be recorded; changes in the prophylaxis regimen should only occur in the event that escalation criteria are met. These study contacts, following study visits 3, 5, 7, and 9 are referred to as study contacts 4, 6, 8, and 10, respectively. (*Note*: Study contact information may be collected at an appropriately scheduled clinic visit, if the subject or the investigator prefers).

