3.7. Description of Study Deviations

3.7.1. Major Protocol Violations

The following are the criteria for the major protocol violations:

- Inclusion or exclusion criteria not met and not exempted;
- Frequent (per clinical judgment) use of nonstudy FVIII concentrates during the study;
- Routine, concomitant treatment with prohibited immunomodulating drugs;
- The use of other investigational agents during the study;

- Frequent (per clinical judgment) use of drugs with antiplatelet activity (eg., aspirin);
- Routinely noncompliant with protocol-specified procedures.

Subjects with major protocol violations should be removed from study per the medical monitor's discretion. Protocol violations or deviations will be listed in the study report.

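### Compliance is summarised without any measure of dosing interval, so schedules that keep the weekly infusion count but break the interval defining Regimen A or B are not identified

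*SAP*

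**What the plan says.** Protocol sections 4, 11.1 and 16.3.2 describe the two prophylaxis regimens. A is defined as "Study drug prophylaxis regimen of 45 ±5 IU/kg, administered twice per week", with this spacing rule in section 16.3.2: "For regimen A, the interval between prophylactic infusions should be 3 to 4 days, and should not exceed 4 days". B is 25 ±5 IU/kg every other day, at intervals of roughly 48 hours. Section 11.1 states that both deliver about 90 IU/kg per week and that what distinguishes them is the schedule.

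Compliance with the assigned regimen is a listed efficacy variable (protocol 22.2). Protocol 22.5.3 plans descriptive statistics to "summarize subject compliance to their assigned prophylaxis regimen (dose [IU/kg] and dose frequency [number of infusions per week", and SAP 3.3.3.7 repeats this: "Descriptive statistics will be provided to summarize subject compliance to their assigned prophylaxis regimen (dose [IU/kg] and dose frequency [number of infusions per week". For individual subjects the SAP adds: "The number of infusions and the number of days (and weeks) on each assigned prophylaxis regimen will be presented for each subject". An exploratory crossover ANOVA on the effect of non-compliance on ABR uses a frequency variable defined so: "Actual treatment frequency will be calculated from the number of infusions divided by the number of weeks on treatment, including non-routine prophylaxis infusions". Neither document plans a comparison of the actual gaps between infusions with the stated intervals.

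The data for such a comparison are collected. Protocol 15.1.6 states: "Subjects will document all of their infusions (dose, time of infusion, and reason) and all bleeding episodes in the Subject Diary". Section 15.1.9 requires the same in segment 2.

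One criterion for a major violation, which removes a subject from the supportive per-protocol set, is "Routinely noncompliant with protocol-specified procedures" (SAP 3.7.1). Protocol 16.8 bases compliance judgments on vial counts, diaries and verbal information, and sets no numerical threshold for noncompliance.

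**The concern.** The secondary objective compares two schedules at nearly equal weekly dose. Dose per infusion and infusions per week describe how much a child took. They do not show when he took it, and timing is what the protocol's interval rule governs. Two children with the same weekly count can have followed very different schedules, and the planned summary would show no difference between them.

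The issue is interpretive. Whatever the A versus B comparison shows, a reader will ask whether the children practised two distinct schedules. The planned compliance tables cannot fully answer that. The exploratory ANOVA has the same limitation, because its measure of actual practice is also a count divided by time.

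**Working it through.** **Inputs.** Dose and interval for A and B: protocol sections 4 and 16.3.2. Weekly dose of about 90 IU/kg: protocol 11.1. Visits needing a 72-hour washout: protocol 15.1.7, 15.1.8, 15.1.10 and 15.1.11. Bleed rates of 5.7 and 7.1 per year from the earlier study: protocol 22.7. Infusions per bleed are not given; I assume 1 to 3.

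**1. The plan's own figure.** Weekly dose = dose per infusion × infusions per week. A: 45 × 2 = 90. B: 25 × 7/2 = 87.5. Both agree with about 90 IU/kg per week. The nominal frequencies are therefore 2.0 (A) and 3.5 (B).

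**2. What the count shows for different spacings.** For a repeating pattern of gaps, infusions per week = 7 × (number of gaps) / (sum of gaps in days).

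| Regimen | Gaps (days) | Infusions per week | Against the interval |
|---|---|---|---|
| A | 3, 4 | 7×2/7 = 2.00 | all within 3 to 4 days |
| A | 2, 5 | 7×2/7 = 2.00 | 50% over 4 days |
| A | 1, 6 | 7×2/7 = 2.00 | 50% over 4 days |
| A | 4 | 7/4 = 1.75 | all within |
| A | 3 | 7/3 = 2.33 | all within |
| A | 5 | 7/5 = 1.40 | 100% over 4 days |
| B | 2 | 7/2 = 3.50 | all 48 hours |
| B | 1, 3 | 7×2/4 = 3.50 | none at 48 hours, 50% at 72 hours |
| B | 3 | 7/3 = 2.33 | all at 72 hours |

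The 1/6 pattern on A also leaves (6 − 4)/7 = 29% of time beyond day 4 after a dose. The count therefore misses breaches that only redistribute infusions, shows breaches that lose them (1.40 and 2.33), and departs from nominal for some A schedules that obey the interval (1.75 and 2.33).

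**3. Week-by-week counts.** The SAP does not say whether infusions per week is a segment average or a weekly tally. A tally would not help here. The 1/6 pattern on A gives exactly 2 in every week. The 1/3 pattern on B gives 3 or 4 in a week, as true every-other-day dosing does.

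**4. Required washouts on B.** Segment 1 has five on-treatment washouts (visits 3, 5, 7, 9, 11) and segment 2 has four (visits 13, 15, 17, 19). Each stretches a 48-hour gap to 72 hours, a loss of one day. Infusions per year = (365.25 − 5)/2 = 180.1 or (365.25 − 4)/2 = 180.6. Divided by 365.25/7 = 52.18 weeks, that is 3.45 or 3.46 against 3.50, a fall of about 1%.

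**5. The exploratory ANOVA.** If its non-routine infusions include bleed treatment, the extra infusions per year run from 5.7 × 1 = 5.7 to 7.1 × 3 = 21.3. Against about 182.6 scheduled on B that is 3% to 12%. Against about 104.4 on A it is 5% to 20%. Missed prophylaxis of that size could be offset in the frequency variable.

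**6. The bleed-timing table (SAP 3.3.3.3).** It classifies bleeds by time since the last prophylaxis dose but has no denominator of time at risk. On A, time beyond 72 hours is 1/7 = 14% with 3/4-day gaps and 3/7 = 43% with 1/6-day gaps. The same number of late bleeds would mean different things in the two cases.

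**The case against.** The strongest reply is that little depends on this. Compliance is one of the other efficacy endpoints, with no hypothesis test (SAP 3.3.3). The equivalence decision rests on the ITT 90% confidence interval, which does not use compliance, and the per-protocol analysis is supportive. All data will be listed, bleed timing is tabulated by regimen, and known non-adherence is a confounder when LETE is judged. This stands as a limit on the consequence. It does not fill the gap, because listings are not a summary and the bleed table covers only the moments when a bleed began.

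Four stronger readings are tempting, and the documents do not support them:

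- *Off-schedule children score as fully compliant.* The plan has no compliance score, threshold or compliant category. Such a child shows the nominal frequency, and only if his breaches preserve the count.
- *Poor spacing biases the trial toward equivalence.* The direction is not established. If spacing matters, a 6-day gap on A would more likely worsen A and widen the difference. Bunching on B could act the other way. The documents give no data on how often either occurs.
- *The per-protocol set cannot remove such children.* SAP 3.7.1 does not tie noncompliance to the weekly count, and protocol 16.8 has diaries inform that judgment. Interval breaches can be recognised; they are simply not summarised.
- *Required washouts distort B's compliance.* The effect is about 1%.

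**Conclusion.** The concern holds in a limited form. Compliance is summarised only by dose and infusions per week, while the interval is part of each regimen's definition and the main contrast between them. Schedules that keep the count but break the interval are not identified: up to half of A's intervals can exceed 4 days at 2.0 per week, and B can show 3.5 per week with no 48-hour interval. In the other direction, A dosed every 4 days meets the interval yet shows 1.75.

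The gap affects the compliance endpoint, the exploratory non-compliance ANOVA and the interpretation of A versus B. It leaves the ITT equivalence interval unchanged. The patterns above are illustrations with fixed gaps, and the documents do not say how common such patterns are. The ANOVA range also assumes 1 to 3 infusions per bleed and that bleed treatment falls within the non-routine infusions. Because the infusion times are already recorded, the plan should be changed.

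**What to change.** In SAP 3.3.3.7:

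- Derive from diary times each interval between consecutive routine prophylaxis infusions.
- Report, per subject and regimen, the distribution of intervals, the longest interval and the percentage within the protocol's own interval. For B, the sponsor should state an analysis tolerance around 48 hours before database lock; the documents give none, and showing the full distribution keeps the result from resting on that choice.
- Flag gaps caused by required pre-visit washouts, surgical periods and time after escalation.
- Count bleed-treatment infusions separately from routine prophylaxis, including in the frequency variable of the exploratory ANOVA.
- Keep infusions per week alongside.

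Make the interval summary available to whoever applies the noncompliance criterion in SAP 3.7.1, but do not add a numerical exclusion cut-off. Protocol 16.8 sets none, and choosing one now, in an open-label study with two interim reports already issued, would add discretion over a post-randomisation exclusion.

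The cost is some SAP text and a little programming on data already collected. Reported compliance may look less favourable.
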